17.4. Exploratory Endpoints

Histological analysis of laser-tissue effects and/or healing response from pre- and post-treatment skin biopsies using light microscopy and/or scanning electron microscopy.

18. Blinded Evaluation

Efficacy endpoints will be determined from the data gathered by blinded evaluators scoring clinical photography. Three qualified, non-treating clinicians will be trained to independently review Baseline and post-treatment photograph sets for each subject. The identity of the subjects will be masked when possible. No information will be provided to the evaluators that may allow them to determine the Baseline from the post-treatment photography. Evaluators will then examine pairs of Baseline and post-treatment photographs presented in a randomized fashion, and be asked to identify which is the Baseline, and to rate any perceived improvement using the Pigment Clearance Scale or Fitzpatrick Wrinkle Scale as appropriate for the condition treated.

19. Statistical Methods

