9.2. Fitzpatrick Wrinkle Scale (FWS)

Improvement in the appearance of facial wrinkles following study treatment will be measured using the validated 9-point Fitzpatrick Wrinkle Scale (FWS) that categorized wrinkle severity from 1=Fine Wrinkles to 9=Deep Wrinkles.¹⁵ The FWS scoring scale is provided in Appendix B.

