17.1. Primary Effectiveness Endpoints

Benign Pigmented Lesions

Mean difference from Baseline to final 12-Week follow-up visit in Pigment Clearance Score as determined by blinded evaluators from clinical photographs.

Wrinkles

Mean difference from Baseline to final 12-Week follow-up in Fitzpatrick Wrinkle Score as determined by blinded evaluators from clinical photographs.

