17.3. Secondary Endpoints

1. Benign Pigmented Lesions

Percentage of subjects demonstrating Pigment Clearance Score (PCS) of 3 or 4 (> 50% improvement) comparing baseline to 12-week follow-up as determined by blinded physician evaluators from clinical photographs

2. Wrinkles

Percentage of subjects demonstrating ≥ 1 score improvement in Fitzpatrick Wrinkle Score (FWS) from baseline to 12-week follow-up visit as determined by agreement of 2 out of 3 blinded physician evaluators from clinical photographs

3. Subject Satisfaction

Mean and distribution of Subject Satisfaction Scores at all visits beyond Treatment Visit #1

4. Subject Pain

Mean and distribution of Subject Pain Scores following each treatment

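### Section 18 does not tell the blinded evaluators to give each photograph its own Fitzpatrick Wrinkle Score, and the rating task it describes does not match the Group B primary endpoint

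*Combined protocol and SAP*

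**What the plan says.** Section 17.1 defines the Group B primary endpoint as "Mean difference from Baseline to final 12-Week follow-up in Fitzpatrick Wrinkle Score as determined by blinded evaluators from clinical photographs". The wrinkle responder endpoint in Section 17.3 is "Percentage of subjects demonstrating ≥ 1 score improvement in Fitzpatrick Wrinkle Score (FWS) from baseline to 12-week follow-up visit", with two of three evaluators agreeing. Section 19.2 calls for the FWS to be evaluated for the peri-orbital region, the peri-oral region and their sum, and states that 1 is the best score. Section 19.3 bases the sample size on a two-sided paired t-test.

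The reading that is to supply these data is described only in Section 18. It opens broadly: "Efficacy endpoints will be determined from the data gathered by blinded evaluators scoring clinical photography". It then gives the task: "Evaluators will then examine pairs of Baseline and post-treatment photographs presented in a randomized fashion". For each pair, evaluators will "be asked to identify which is the Baseline, and to rate any perceived improvement using the Pigment Clearance Scale or Fitzpatrick Wrinkle Scale", whichever scale suits the condition treated. Three non-treating clinicians do this independently, and nothing that would reveal which photograph is Baseline is given to them.

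Section 9.2 describes the FWS as a scale that "categorized wrinkle severity from 1=Fine Wrinkles to 9=Deep Wrinkles". Appendix B defines every value by wrinkle depth and elastosis. The only other FWS assessment in the protocol is at the Screening Visit (Section 10.1), and it is not a blinded photograph score.

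**The concern.** The Pigment Clearance Scale (PCS) grades improvement, so one rating per pair suits it. The FWS grades severity, and change on it exists only as the difference between two scores. One sentence in Section 18 sets the same task for both scales, and for wrinkles the task does not yield the two scores.

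Two things are at stake. First, three evaluators given this instruction could do different things: score both photographs and subtract, judge the change directly, or record only gains. The primary outcome would then not be one defined measurement. Second, even if every evaluator supplies two scores, they are formed side by side while the evaluator decides which photograph is earlier, under an instruction that mentions improvement and not worsening. In a single-arm study where each subject is his or her own control, any upward bias in the change goes directly into the treatment effect.

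**Working it through.** **1. What the analysis needs and what Section 18 asks for**

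| Item | Needed (Sections 17.1, 17.3, 19.2, 19.3) | Section 18, read literally |
|---|---|---|
| Unit scored | Each photograph | Each pair |
| Quantity | Severity, 1-9 | Perceived improvement |
| Values per subject per evaluator | 2 regions × 2 time points = 4 | 1, no region named |
| Worsening | A change of unfavourable sign | Not asked for |
| Baseline wrongly identified | Should not matter | No rule |
| Three evaluators to one mean | A rule is needed | None; 2-of-3 agreement covers the responder endpoint only |

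**2. The plan's own figure**

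Inputs from Section 19.3: n = 34, improvement δ = 1 point, SD of the change = 2, two-sided α = 0.05, paired t-test.

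- Noncentrality = (δ/SD) × √n = (1/2) × √34 = 2.92.
- Critical t on 33 degrees of freedom = 2.0345.
- Power from the noncentral t distribution = 80.8% (n = 33 gives 79.5%). The stated 34 and 80% reproduce.
- Smallest significant mean change = 2.0345 × 2/√34 = 0.70 points.

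Nothing is wrong with these figures. They presuppose two scores per subject.

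**3. How much the reading rule can matter**

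The documents give no figure for reader bias or for how often Baseline is misidentified. The inputs below are assumptions that show a range.

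*(a) Modest upward bias, no true effect.* Suppose side-by-side reading adds b points to the mean change, with SD 2 and n = 34. The chance of a significant result is the power formula of step 2 with b in place of δ:

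- b = 0: 5%
- b = 0.25: 10.9%
- b = 0.5: 29.3%

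*(b) Extreme upward case, no true effect.* Suppose the difference D is normal with mean 0 and SD 2, the evaluator always calls the worse-looking photograph Baseline, and the rating is not re-signed against the true labels. The recorded improvement is then |D|.

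- Mean = √(2/π) × 2 = 0.798 × 2 = 1.60 points.
- SD = 2 × √(1 − 2/π) = 1.21.
- Threshold for significance = 2.0345 × 1.21/√34 = 0.42.

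An ineffective treatment would be declared effective almost every time.

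*(c) The opposite direction.* Suppose the true improvement is 1 point and a fraction m of changes is recorded with the sign reversed, independently of their size. The mean is 1 − 2m and the variance is 4 + 1 − (1 − 2m)².

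| m | Mean | SD | Power, n = 34 |
|---|---|---|---|
| 0 | 1.0 | 2.00 | 80.8% |
| 0.1 | 0.8 | 2.09 | 58% |
| 0.2 | 0.6 | 2.15 | 35% |
| 0.3 | 0.4 | 2.20 | 18% |

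These cases do not predict what will happen. They show that the Group B result could move in either direction according to a rule that Section 18 leaves unstated.

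**The case against.** The strongest reply is that two scores were plainly intended. Section 18 begins by speaking of scoring photographs. Section 9.2 says "Improvement in the appearance of facial wrinkles following study treatment will be measured using the validated 9-point Fitzpatrick Wrinkle Scale" in the same sentence that calls it a severity scale, so rating improvement with the FWS may simply be shorthand for a change in severity. The endpoints, the hypotheses and the paired t-test all presuppose an FWS at both visits. Evaluators are to be trained, and Section 19.1 promises a statistical analysis plan before study initiation, so the detail may sit there. Paired reading is also a legitimate method: readings are independent between evaluators, order is randomized, and a paired t-test does not require a subject's two scores to be independent.

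Most of this stands as evidence of intent, and it limits the conclusion. A reader might infer that neither photograph is scored, so that the endpoint cannot be computed. The documents leave the step unstated; they do not rule it out. A reader might also infer that, because the scale starts at 1, every subject would count as a 1-point responder and exceed the 0.70 threshold. That requires entering improvement as a value from 1 to 9 with higher meaning better, which conflicts with Section 19.2 (1 is best) and with Appendix B. The 0.70 is correct arithmetic but reveals no error in the plan. Nor does Section 18 say that Baseline must be declared before rating; it only lists the two tasks together.

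The reply does not supply the missing step. No section tells the blinded evaluators to score each photograph, names the regions, or says what happens when Baseline is misidentified. The promise of a later plan does not change what Section 18 instructs.

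**Conclusion.** The point holds as a mismatch between the instruction and the endpoint. It does not show that the data cannot be obtained. Section 18, followed as written, collects one improvement rating per pair on a scale that grades severity; the Group B primary, the responder endpoint and the paired t-test of Section 19.3 need a score at each time point. If evaluators fill the gap themselves by scoring side by side, upward bias is possible and unmeasured. Under the assumptions shown, 0.25 to 0.5 points of bias would raise the false-positive rate from 5% to between 11% and 29%.

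The gap affects every wrinkle subject. The figure 34 is the evaluable number required for power, not a stated Group B enrolment; the protocol allows up to 160 subjects overall. The sample-size calculation is sound. Because this governs how a primary outcome is acquired, it should be settled before any photograph is read.

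Section 19.4 attaches the paired t-test to the pigment score and the exact binomial test to the wrinkle score, the reverse of Section 19.3. That is a separate matter; Section 19.3 is followed here.

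**What to change.** For Group B, rewrite Section 18 to state that:

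- each evaluator assigns a 1-9 FWS to each masked Baseline and 12-week photograph, separately for the peri-orbital and peri-oral regions;
- photographs are shown singly and unlabelled, in random order across subjects and visits, before any pair is displayed;
- change is computed afterwards from the true visit labels, so that worsening is recorded and a misidentified Baseline cannot alter a score;
- the three evaluators' scores are combined by a named rule for the mean change (for example, their average), with 2-of-3 agreement kept for the responder endpoint.

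Keep paired viewing for the PCS, where an improvement rating is what the scale records.

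If the sponsor prefers paired viewing for wrinkles as well, the minimum is to require a separate FWS for each photograph, re-signed from the true labels. That closes the gap in the data but leaves the possible side-by-side bias.

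The cost is new evaluator instructions, a different presentation order and modest extra reading time. The photographs and the three evaluators stay the same. The 34 evaluable subjects and 80% power are unchanged if the SD of the change is still 2. That should be checked, since single-photograph reading may give a different SD from paired reading.

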9.1. Pigment Clearance Score (PCS)

Clearance of pigment following study treatment will be measured using a validated 5-point Pigment Clearance Scale (PCS) that categorizes improvement in the appearance of pigmented lesions from 0=0% or No Improvement to 4=75-100% or Excellent Improvement.¹⁴ The PCS scoring scale is provided in Appendix A.

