10.3. Follow-Up Visits

Subjects will be scheduled for follow-up visits at 4 ± 1 weeks, 8 ± 2 weeks, and 12 ± 2 weeks after their final study treatment visit, or approximately 1, 2 and 3 months. Additional visits may be scheduled by the Investigator as needed.

Photography

Treatment areas will be photographed at all follow-up visits using the same camera settings used previously at Baseline and Treatment Visits.

Subject Satisfaction

Subjects will be asked to rate their level of satisfaction with the study treatments thus far at each follow-up visit using the Subject Satisfaction Scale provided in Appendix C.

Skin Biopsy (optional)

Subjects who have provided prior written consent may have one or more skin biopsy taken from the treated area at the discretion of the Investigator. Biopsy procedure details are provided in the Treatment Visit section above.

11. Schedule of Events

The Study Schedule of Events is provided in Table 1.

NOTE: The Screening and Baseline / Treatment #1 Visits may be combined in the same visit.

NOTE: Fewer than four (4) Treatment Visits may be required to reach maximum expected clinical results in some subjects. Treatments may therefore be stopped, and subject placed into the Follow-Up phase at the discretion of the Investigator.

Table 1: Study Visits and Schedule of Events

Activity	Screening	Baseline Tx 1	Tx 2	Tx 3	Tx 4	1 Month Follow- Up	2 Month Follow- Up	3 Month Follow- Up
	0 to -2 Weeks	Day 0	Week 6 ± 2 Weeks	Week 12 ± 2 Weeks	Week 18 ± 2 Weeks	Week 22 ± 2 Weeks	Week 26 ± 2 Weeks	Week 30 ± 4 Weeks
Informed Consent	X							
Medical History/Concomitant Medications	X							
Inclusion/Exclusion Criteria	X							
Treatment Site ID	X							
Pregnancy Test	X	X	X	X	X			
Skin Biopsy (Optional)		X	X	X	X	X	X	X
Telephone Contact*		X	X	X	X			
Photography		X	X	X	X	X	X	X
Laser Treatment		X	X	X	X			
Subject Pain Score		X	X	X	X			
Subject Satisfaction			X	X	X	X	X	X
Safety Assessment (LSR, ADE, UADE)		X	X	X	X	X	X	X
Concomitant Medications	X	X	X	X	X	X	X	X
Study Exit								X

*10 Days post-treatment (+/- 7 Days)

12. Study Compliance

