30.1. Appendix A: Pigment Clearance Score Pigment Score

Score	Clearance	Description
1	0% - 24%	Poor response
2	25 - 49%	Fair Response
3	50 - 74%	Good response
4	75 - 94%	Excellent response
5	$\geq 95\%$	Complete response

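### Section 18 has blinded evaluators pick the Baseline photo and rate improvement on a pigment scale with no worsening grade, but no rule says how a wrongly identified pair is scored

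*Combined protocol and SAP*

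**What the plan says.** **Reading procedure (Section 18).** "Three qualified, non-treating clinicians will be trained to independently review Baseline and post-treatment photograph sets for each subject". On order masking: "No information will be provided to the evaluators that may allow them to determine the Baseline from the post-treatment photography". Faced with a randomized pair, evaluators will "be asked to identify which is the Baseline, and to rate any perceived improvement" on the pigment or the wrinkle scale, whichever fits. The improvement grade is therefore relative to the photo that the evaluator took to be Baseline.

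**The scales.** Section 9.1 runs the PCS "from 0=0% or No Improvement to 4=75-100% or Excellent Improvement". Appendix A runs it from 1 to 5, and its lowest grade, 0% to 24% clearance, is labelled "Poor response". Neither version has a grade for worsening. The Fitzpatrick Wrinkle Score (FWS) differs in kind: Section 9.2 describes a scale "that categorized wrinkle severity from 1=Fine Wrinkles to 9=Deep Wrinkles", which grades one photo at a time.

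**Use of the scores.** Section 17.1 makes the mean PCS difference at 12 weeks the primary pigment endpoint, and 17.3 lists the responder percentage as secondary. Sections 19.2 and 19.3, however, build the Group A hypothesis and sample size on the responder rate, and 19.3 treats it as the primary endpoint. Section 19.4 gives the pigment score a paired t-test and the wrinkle score an exact binomial test, the reverse of 19.3. A 2-of-3 evaluator rule appears in 17.3 for wrinkles only.

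**What is absent.** Nothing in Sections 17 to 19 uses the Baseline pick or says what happens when it is wrong. Section 19.1 promises a SAP before study start, but no separate SAP text is among the documents.

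**The concern.** Collecting the Baseline pick is good practice, but it protects the result only if a wrong pick changes the score. Suppose the treated area looks darker at 12 weeks, and the evaluator takes the darker photo as Baseline. The true change is a worsening, yet the form offers only grades of improvement. Section 10.2 lists hyperpigmentation as an anticipated device effect, so such pairs are foreseeable.

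The error has one direction: a reversed pair can be recorded as no change or as benefit, never as harm. Subjects are their own controls (Section 5), so there is no comparator arm in which the same reading error would occur and cancel. The two pigment analyses are exposed differently. The mean PCS moves with any perceived difference. The responder rate moves only if the reversed difference is graded Good or better.

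**Working it through.** **1. The plan's own figure.** Section 19.3 gives 30 evaluable subjects, 50% against 75%, a two-sided exact binomial test at 5%, and 80% power. The observed rate needed for success is blacked out, so I derived it as the smallest r with P(X ≥ r | 30, 0.50) ≤ 0.025.

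- r = 20: 0.0494, too large.
- r = 21: 0.0214 (two-sided 0.0428); power P(X ≥ 21 | 30, 0.75) = 0.803.

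The stated 80% reproduces with success at 21/30.

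**2. Responder rate, one reading per subject.** Assume a true rate of 50%, and let m be the share of non-responders who are read in reverse *and* graded Good or better. The documents give no value for m. The observed rate is q = 0.50 + 0.50m, and the false-success chance is P(X ≥ 21 | 30, q).

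| m | q | False-success chance |
|---|---|---|
| 0 | 0.500 | 2.1% |
| 1% | 0.505 | 2.4% |
| 2% | 0.510 | 2.8% |
| 5% | 0.525 | 4.0% |
| 10% | 0.550 | 6.9% |

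**3. If a 2-of-3 rule applied to pigment.** Let each evaluator independently reverse a non-responder and grade it Good or better with probability e. Then m = 3e²(1 − e) + e³.

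| e | m | q | False-success chance |
|---|---|---|---|
| 5% | 0.00725 | 0.5036 | 2.3% |
| 10% | 0.028 | 0.514 | 3.1% |
| 20% | 0.104 | 0.552 | 7.2% |

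These are smaller than the single-reading results at the same rates (4.0%, 6.9% and, at 20%, 17.6%). If the evaluators are misled by the same feature of a photo, the protection shrinks.

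**4. How large a reversal has to be.** Good means at least 50% clearance. For a reversed pair to reach it, the true Baseline photo must show at most half the pigment of the 12-week photo, so visible pigment must have at least doubled. A little-changed pair read in reverse gets a low grade and remains a non-response.

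**5. Mean PCS.** No such threshold applies here. As an illustration, assume no true effect, n = 30, the 0–4 scale of Section 9.1 with scores of 0 or 1 only, a t-test against 0, and evaluators who take the darker photo as Baseline. A share d of pairs shows a chance photographic difference, equally likely in either direction. Every such pair scores +1, so the mean is biased from 0 to d.

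With k pairs scored 1, the mean is k/30 and the SD is √[k(1 − k/30)/29]. For k = 4 the mean is 0.133, the SD 0.346 and the standard error 0.346/√30 = 0.063, so t = 2.11, above the critical 2.05. For k = 3, t = 1.80. False significance is therefore P(K ≥ 4), where K is binomial(30, d). If wrong picks are set to 0 instead, K is binomial(30, d/2). If signs are restored, scores are +1 or −1 with probability d/2 each, and the upper tail is found by enumeration.

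| d | As written | Wrong pick set to 0 | Sign restored |
|---|---|---|---|
| 10% | 35% | 6% | 1.5% |
| 20% | 88% | 35% | 2.4% |

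Setting wrong picks to the lowest grade leaves a bias of d/2 in the mean. Reversing the sign removes it.

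**6. Cost of the responder rule.** If a share f of true responders is misidentified and counted as non-response, the observed rate at the alternative is 0.75(1 − f). For f = 2% this is 0.735 and power is 0.745. For f = 5% it is 0.7125 and power is 0.647.

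**The case against.** The strongest reply is that the documents are silent, not wrong. Asking for the Baseline pick has an obvious use as a check on the grade, and the promised SAP could contain the rule. That stands as far as it goes. A reader might infer that reversed pairs *are* scored as benefit and that the responder rate *is* inflated. The text supports neither: it shows only that nothing prevents this.

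The effect on the responder rate is also easy to overstate. A false responder needs apparent pigment to have at least doubled, and Section 21.1 places hyperpigmentation among the less common responses. Taking m as 20% or 30% gives false-success chances of 17.6% and 35.8%, but that means 10% or 15% of all subjects reversed and graded Good or better, and no figure in the documents supports it. The missing worsening grade alone does not move the responder rate either, because a worsened subject who is correctly identified is already a non-responder. Finally, the responder rate is the tested quantity only in 19.2 and 19.3. All of this stands, and it limits the size of the point for that analysis. It does not help the mean PCS.

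Two further inferences are tempting. One is that the FWS analysis has the same fault. It largely does not: a planned change from Baseline with a paired t-test (17.1, 19.3) implies a score for each photo, from which a signed change is recoverable. Only the wording of Section 18 needs tightening. The other is that biopsy marks undo the masking, since subjects "may have one or more skin biopsy taken from the treated area at the discretion of the Investigator". Biopsies are optional and may lie only near the area (10.2), and a mark that reveals the later photo would make a reversal less likely. That is a separate, minor matter.

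**Conclusion.** The point holds as a missing scoring rule with a one-directional consequence. Under the text as it stands, a reversed pigment pair can only be neutral or favourable to the device, and there is no control arm to absorb the error.

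The mean PCS is the more exposed analysis. Any perceived difference read in reverse pushes it upward. The error rates in step 5 rest on deliberately simple assumptions, including a test against 0, which the plan does not specify; they show how the bias works and do not forecast its size.

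For the responder rate the effect is modest at plausible-looking values: from 2.1% to between 2.4% and 6.9% for m from 1% to 10%. That rests on n = 30, a true rate of 50%, a derived cut-off of 21/30 and one reading per subject, and it would be smaller under a 2-of-3 rule. The documents give no reversal rate, so the range is conditional. Actual inflation is not established. The rule should nevertheless be written before any photograph is read, because it is cheap and cannot be chosen credibly afterwards.

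**What to change.** In Section 18 and the SAP, before any reading:

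1. After unmasking, compare each evaluator's Baseline pick with the true photo dates.
2. In the responder analysis, count a wrong pick as a non-response.
3. In the mean PCS analysis, reverse the sign of the grade for a wrong pick. This needs a scale anchored at zero, so the 0–4 version in 9.1 and the 1–5 version in Appendix A must be reconciled first.
4. Report the misidentification rate.
5. State whether these rules apply to each evaluator's reading before the three PCS grades are combined, and how they are combined, since the 2-of-3 rule now covers wrinkles only.
6. State that each photo receives its own FWS score, with change computed from the true dates.

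This changes wording and the reading form, and adds no visits or subjects. It does have a statistical price: true responders who are misidentified also become non-responders, so power at 75% falls from 0.803 to 0.745 if 2% of them are reversed and to 0.647 if 5% are. If the sponsor expects misidentification of that order, the 30 evaluable subjects for Group A should be reconsidered; the overall ceiling of 160 subjects leaves room.
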